## 7.5. Safety Assessments

### 7.5.1. Adverse Events

Adverse events will be monitored from the time the subject signs the ICF. Subjects (parent or legal guardian) will be instructed to report all AEs during the study and will be assessed for the occurrence of AEs throughout the study. In order to avoid bias in eliciting AEs, subjects will be asked general, nonleading questions such as "How are you feeling?" All AEs (serious and nonserious) must be recorded on the source documents and eCRFs regardless of the assumption of a causal relationship with the study drug. The definition, reporting, and recording requirements for AEs are described in Section 8.

### 7.5.2. Physical Examination

The targeted physical examination will be a symptom-directed evaluation conducted by the investigator or a medically qualified designee. The targeted physical examination will include assessment(s) of the body systems or organs, as indicated by subject symptoms, AEs, or other findings. Clinically notable abnormalities that are considered clinically significant in the judgment of the investigator are to be reported as AEs.

Height and weight will be assessed and compared with the standard pediatric growth charts.

### 7.5.3. Vital Signs

Vital sign measurements include blood pressure, pulse, respiratory rate, body temperature, and body weight. Blood pressure and pulse will be taken with the subject in the recumbent, semirecumbent, or sitting position. Clinically notable abnormalities that are considered clinically significant in the judgment of the investigator are to be reported as AEs.

### 7.5.4. Eastern Cooperative Oncology Group and Lansky Scale Performance Status

ECOG performance status ([Oken et al 1982; Table 8](#)) for children  $\geq$  16 years old and Lansky Scale performance status ([Lansky et al 1987; Table 9](#)) for children  $<$  16 years old will be assessed at screening and other study visits per [Table 5](#). Performance status must be assessed by a medically qualified individual and recorded in the eCRF.

**Table 8: Eastern Cooperative Oncology Group Performance Status Grades (Age  $\geq$  16 Years)**

Grade	Performance Status
0	Fully active, able to carry on all predisease performance without restriction.
1	Restricted in physically strenuous activity but ambulatory and able to carry out work of a light or sedentary nature, eg, light house work, office work.
2	Ambulatory and capable of all self-care but unable to carry out any work activities. Up and about more than 50% of waking hours.
3	Capable of only limited self-care, confined to bed or chair more than 50% of waking hours.
4	Completely disabled. Cannot carry on any self-care. Totally confined to bed or chair.
5	Dead.

**Table 9: Lansky Scale (Age < 16 Years)**

Able to carry on normal activity; no special care is needed	
100	Fully active.
90	Minor restriction in physically strenuous play.
80	Restricted in strenuous play, tires more easily, otherwise active.
Mild to moderate restriction	
70	Both greater restrictions of and less time spent in active play.
60	Ambulatory up to 50% of time, limited active play with assistance/supervision.
50	Considerable assistance required for any active play, fully able to engage in quiet play.
Moderate to severe restriction	
40	Able to initiate quiet activities.
30	Needs considerable assistance for quiet activity.
20	Limited to very passive activity initiated by others (eg, TV).
10	Completely disabled, not even passive play.

#### **7.5.5. Twelve-Lead Electrocardiograms**

A 12-lead ECG will be performed during screening with the subject in a recumbent or semirecumbent position after approximately 5 minutes of rest.

The 12-lead ECG will be interpreted by the investigator at the site and will be used for immediate subject management. The decision to include or exclude a subject or withdraw a subject from the study based on an ECG flagged as "Abnormal, Clinically Significant" is the responsibility of the investigator, in consultation with the sponsor's medical monitor, as appropriate.

Electrocardiograms that are identified as abnormal and clinically meaningful compared with the screening assessment should be reported as AEs. For such AEs, the findings of the abnormal ECGs and the corresponding baseline ECG findings must be reported in the eCRF.

An additional ECG will be performed at the EOT visit; additional ECGs may be performed at the investigator's discretion as clinically indicated.

#### **7.5.6. Laboratory Assessments**

Blood draws for laboratory assessments will occur at study visits indicated in [Table 6](#). Blood draws should be completed whenever possible before the subject receives the morning dose of study drug. Specific laboratory assessments are listed in [Table 7](#).

All laboratory assessments will be performed at a local (site) laboratory using institutional best practices. Results and normal reference ranges will be entered into the eCRF.

#### **7.5.6.1. Chemistry**

All chemistry panel assessments will be performed at a local (site) laboratory from blood samples collected using institutional best practices before administration of study drug. Results and normal reference ranges will be entered into the eCRF.

#### **7.5.6.2. Hematology**

Hematology assessments, including complete blood count with differential, will be performed at a local (site) laboratory using institutional best practices before administration of study drug. Results and normal reference ranges will be entered into the eCRF.

#### **7.5.6.3. Pregnancy Testing**

A serum pregnancy test will be required for all females of childbearing potential during screening and at the EOT visit; this may apply to Cohort 1. Urine pregnancy tests will be conducted every 28 days. Urine pregnancy tests will be performed locally. If a urine pregnancy test is positive, the results should be confirmed with a serum pregnancy test.

If the serum pregnancy test is negative after a urine test was positive, the investigator will assess the potential benefit/risk to the subject and determine whether it is in the subject's best interest to resume study drug and continue participation in the study.

#### **7.5.6.4. Hepatitis Screening**

Subjects with active HBV or HCV infection that requires treatment or who are at risk for HBV reactivation are excluded from the study. At risk for HBV reactivation is defined as hepatitis B surface antigen positive or anti-hepatitis B core antibody positive. Prior test results obtained as part of standard of care before allo-HSCT confirming that a subject is immune and not at risk for reactivation (ie, hepatitis B surface antigen negative, surface antibody positive) may be used for purposes of eligibility, and tests do not need to be repeated. Subjects whose immune status is unknown or uncertain must have results confirming immune status before enrollment.

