### **3.2. Subject Exclusion Criteria**

A subject who meets any of the following criteria will be excluded from the study:

1. More than 1 allo-HSCT.
2. Received more than 2 days of systemic corticosteroids for aGVHD before the first study drug administration.
3. Presence of GVHD overlap syndrome.
4. Presence of an active uncontrolled infection, defined as hemodynamic instability attributable to sepsis or new symptoms, worsening physical signs, or radiographic findings attributable to infection. Persisting fever without signs or symptoms will not be interpreted as an active uncontrolled infection.
5. Known HIV infection.
6. Active hepatitis B virus (HBV) or hepatitis C virus (HCV) infection that requires treatment or at risk for HBV reactivation (ie, positive hepatitis B surface antigen [HBsAg] and/or positive total hepatitis B core antibody). Prior test results obtained as part of standard of care before allo-HSCT confirming that a subject is immune and not at risk for reactivation may be used for purposes of eligibility, and tests do not need to be repeated.
7. Subjects with evidence of relapsed primary disease, or subjects who have been treated for relapse after the allo-HSCT was performed.
8. Any corticosteroid therapy for indications other than GVHD at doses  $> 1$  mg/kg per day of methylprednisolone (or equivalent) within 7 days of the first study drug administration.
9. Severe organ dysfunction unrelated to underlying GVHD, including the following:
  - a. Abnormal liver function, defined as total bilirubin  $> 1.5 \times$  ULN (unless elevated bilirubin is attributed to Gilbert's syndrome) and/or ALT/AST  $> 2.5 \times$  ULN.
  - b. Clinically significant or uncontrolled cardiovascular disease, including unstable angina, acute myocardial infarction within 6 months from Study Day 1, New York Heart Association Class III or IV congestive heart failure, circulatory collapse requiring vasopressor or inotropic support, or arrhythmia that requires therapy.
  - c. Clinically significant respiratory disease that requires mechanical ventilation support or  $\geq 50\%$  oxygen.
10. May be applicable for Cohort 1: currently breast feeding.

11. Receipt of live (including attenuated) vaccines or anticipation of need for such vaccines during the study.
12. Receipt of JAK inhibitor therapy after allo-HSCT for any indication. Treatment with a JAK inhibitor before allo-HSCT is permitted.

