**Table 6: Laboratory Assessments**

Visit Day Item	Section	Screening	Treatment a												EOT e	Re-Treatment f	Safety Follow-Up g	GVHD Follow-Up h									
		-28 to -1	D1 b	D7	D14	D21	D28	D35	D42	D49	D56 c	D100	D180	D365 d													
Chemistry panel h	7.5.6.1	X	X	X	X	X	X	X	X	X	X i	X i	X	X	X	X	X j										
Hematology h	7.5.6.2	X	X	X	X	X	X	X	X	X	X i		X	X	X	X											
Hepatitis screening	7.5.6.4	X k																									
HIV screening	7.5.6.5	X k																									
Adenovirus, CMV, and EBV blood DNA-PCR	7.5.6.6		X l	X m										X	X m												
Serum pregnancy test (childbearing females only); may apply only to Cohort 1	7.5.6.3	X													X												
Urine pregnancy test n (childbearing females only); may apply only to Cohort 1	7.5.6.3		X																								
PK assessment h,o	7.7		X p	X			X p																				

a A ± 3-day window is permitted to facilitate scheduling during the treatment period.

b Day 1 laboratory assessments do not need to be repeated if screening assessments were performed within the preceding 7 days, except for PK.

c After Day 56, visits will occur every 28 days and will include all Day 56 assessments.

d The Day 365 visit will also serve as the regularly scheduled visit occurring every 28 days after Day 56 (ie, Day 364).

e A ± 7-day window is permitted. A second EOT should occur if the subject restarts itacitinib and subsequently discontinues treatment.

f Re-treatment assessments occur every 28 days ± 3 days.

g 30 to 35 days after EOT.

h Efforts should be made to use the minimal possible blood volume for performing these tests.

i Does not need to be repeated if test is performed within 7 days.

j Liver testing including total bilirubin.

k Test results before transplantation are acceptable.

l PCR test results are not required for subject eligibility.

m To be performed weekly as long as GVHD is active and then as clinically indicated.

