**Table 7: Clinical Laboratory Analytes**

Serum Chemistries	Hematology a	Other
Albumin	Hematocrit	Serum pregnancy test b
Alkaline phosphatase	Hemoglobin	Urine pregnancy test b
ALT	Mean corpuscular volume	
AST	Reticulocytes	
Bicarbonate or CO 2	Platelet count	
Blood urea nitrogen	Red blood cell count	
Calcium	White blood cell count	
Chloride	White blood cell differential (5 parts):	Hepatitis and HIV Screening Testsc
Creatinine	
 
• Basophils
 
• Eosinophils
 
• Lymphocytes
 
• Monocytes
 
• Neutrophils
 
	Hepatitis B surface antigen Hepatitis B surface antibody Hepatitis B core antibody HCV antibody HCV-RNA HBV-DNA HIV
Glucose		Adenovirus, EBV, and CMV Assessments
Lactate dehydrogenase		Adenovirus-DNA EBV-DNA CMV-DNA
Lipid profile (total cholesterol, high-density lipoprotein, low-density lipoprotein, and triglycerides)		
Phosphorus		
Potassium		
Sodium		
Total bilirubin		
Total protein		

ALT = alanine aminotransferase; AST = aspartate aminotransferase; CMV= cytomegalovirus; EBV= Epstein-Barr virus; HBV = hepatitis B virus; HCV = hepatitis C virus.

a Hematology and chemistry assessments will be performed locally.

b May be applicable to Cohort 1 only.

c Test results obtained before transplantation are acceptable.

All possible measures should be taken to reduce pain and discomfort (eg, use of local anesthesia before venipunctures, noninvasive measure should be preferred and timing coordinated with daily activities as far as possible; [European Commission 2017](#)). Physical pain and discomfort intensity must be assessed and regularly monitored and treated according to local appropriate guidance (eg, ethical considerations for clinical studies on medicinal products conducted with minors), particularly in neonates and children who cannot express it verbally. In order to minimize pain, discomfort, and fear, facilities should be appropriate to childcare, and the personnel should be trained to look after children and supervised by experienced health care professionals. The investigational site's staff should be trained to communicate with both the parents/legally designated representative and the children.

The degree of burden and risk threshold will be constantly monitored by the investigator.

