### **4. Synopsis; Section 3.2, Subject Exclusion Criteria; Section 7.5.6.4, Hepatitis Screening**

**Description of change:** Reworded Criterion 6 so that subjects with active HBV or HCV infection that requires treatment or who are at risk for HBV reactivation are not eligible for this study.

**Rationale for change:** There is a risk for reactivation in subjects who would require frequent viral DNA monitoring. Because hepatitis positivity is extremely rare in the pediatric population and the blood volume amounts that can be withdrawn in this population are limited, pediatric experts advised to exclude those patients from the study.

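### The hepatitis B prior-results waiver in Section 7.5.6.4 omits core antibody, so a child never tested for it can be cleared although Exclusion 6 turns on that marker

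*Combined protocol and SAP*

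**What the plan says.** Exclusion 6 (Section 3.2, repeated in the synopsis) bars children who are "at risk for HBV reactivation (ie, positive hepatitis B surface antigen [HBsAg] and/or positive total hepatitis B core antibody". Section 7.5.6.4 uses the same two markers: "At risk for HBV reactivation is defined as hepatitis B surface antigen positive or anti-hepatitis B core antibody positive".

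Both places let standard-of-care results from before the transplant stand in for new testing if they show the child to be immune and not at risk. Only Section 7.5.6.4 says what such results look like: "ie, hepatitis B surface antigen negative, surface antibody positive) may be used for purposes of eligibility, and tests do not need to be repeated". It then adds a fallback: "Subjects whose immune status is unknown or uncertain must have results confirming immune status before enrollment".

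The hepatitis and HIV screening panel in Table 7 reads: "Hepatitis B surface antigen Hepatitis B surface antibody Hepatitis B core antibody HCV antibody HCV-RNA HBV-DNA HIV". Its footnote says "Test results obtained before transplantation are acceptable", and the Table 6 footnote on the screening rows says "Test results before transplantation are acceptable". Table 6 marks hepatitis testing at the screening visit only.

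**The concern.** The waiver describes a child who is not at risk without using one of the two markers that define risk. In its place stands anti-HBs, which appears in neither definition. Because the pattern is introduced by ie, it reads as the specification and not as an example. A site that looks up what the unexplained waiver in Exclusion 6 means will find this parenthesis.

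The criterion protects children who will receive itacitinib, for which Sections 1.3.2 and 1.5 warn of a possible increase in infections, on top of systemic corticosteroids. The Amendment 2 rationale, cited here only for intent, reads: "There is a risk for reactivation in subjects who would require frequent viral DNA monitoring". It adds that blood volumes in this population are limited, and that at-risk children were excluded for these reasons. A child admitted with an undetected positive anti-HBc would have no scheduled hepatitis test after screening. Section 3 permits no eligibility deviations, so the criterion should lead every site to the same decision.

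**Working it through.** There is no figure to reproduce; the check is logical. The inputs are the risk definition (Exclusion 6 and Section 7.5.6.4), the waiver pattern and the fallback sentence (both Section 7.5.6.4), and the panel and footnotes (Tables 6 and 7).

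HBsAg and anti-HBs are each taken as negative or positive. Anti-HBc needs three levels: negative, positive, and no result on file. That gives 2 × 2 × 3 = 12 patterns. The waiver fixes HBsAg negative and anti-HBs positive, so 1 × 1 × 3 = 3 patterns meet its parenthesis:

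| HBsAg | anti-HBs | anti-HBc | Risk definition and Exclusion 6 | Waiver parenthesis |
|---|---|---|---|---|
| negative | positive | negative | not at risk | met |
| negative | positive | positive | at risk, excluded | met on its wording |
| negative | positive | no result | cannot be determined | met |

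1. In the first row the rules agree.
2. In the second row two adjacent sentences of Section 7.5.6.4 point in opposite directions. Eligibility is still settled: results that include a positive anti-HBc cannot show a child to be not at risk, and Exclusion 6 bars the child outright.
3. In the third row the parenthesis treats the two results as sufficient, while Exclusion 6 cannot be applied without the third. This is the operative gap.

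Next, does any other text force the missing test in the third row?

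- The fallback sentence does not. Its trigger is unknown or uncertain immune status, and the parenthesis has just classed this child as immune. What it asks for is immune status, not anti-HBc status. The HIV fallback in Section 7.5.6.5 does ask for the result that decides the exclusion, namely a negative HIV status.
- The footnotes to Tables 6 and 7 do not. They allow results from before the transplant but do not say which results must be on file.
- Table 7 comes closest, because it lists anti-HBc and HBV-DNA. But it does not say that the panel must be completed when the Section 7.5.6.4 waiver applies.

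Finally, is there a later safeguard? Table 6 has one hepatitis row, marked at screening. The repeated viral PCR row covers adenovirus, CMV and EBV, not HBV. The count of scheduled HBV tests after screening is therefore 0.

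**The case against.** The strongest reply rests on Table 7. Anti-HBc is in the screening panel, and language about not repeating tests can apply only to tests already done. The footnotes say when a test may have been performed; they do not shorten the panel. On that reading, a careful site with no anti-HBc result would obtain one. This is a reasonable reading, and it lowers the chance of a wrong enrollment. It does not remove the conflict, because Section 7.5.6.4 still presents two markers as enough for eligibility and no sentence gives the panel precedence.

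Three stronger conclusions are tempting, and the documents do not support them.

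- A reader might infer that every HBsAg-negative, anti-HBs-positive, anti-HBc-positive child would be enrolled. Where the positive anti-HBc is known, Exclusion 6 and the risk definition both bar the child. Likewise, two sites would reach opposite decisions on the same child only if the anti-HBc result is missing and one of them does not work from Table 7.
- A reader might infer that a child negative for all hepatitis B markers could never satisfy the fallback sentence. That sentence applies only when status is unknown or uncertain. An all-negative result is a known status, and the sentence does not demand that the status be immune.
- A reader might infer that the protocol has no HBV-DNA test at all. Table 7 lists one at screening; what is absent is any scheduled test afterwards.

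**Conclusion.** The point holds as an internal contradiction in an eligibility criterion: Section 7.5.6.4 conflicts with its own preceding sentence and with Exclusion 6. Its practical reach is one situation, a child whose pre-transplant file has HBsAg negative and anti-HBs positive but no anti-HBc result.

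The number of such children among the approximately 150 planned cannot be computed. The documents give neither the share of files lacking anti-HBc nor the share of those children who would test positive. It is probably small, since the Amendment 2 rationale describes hepatitis positivity in children as extremely rare. No endpoint, estimate or decision rule is affected. The conclusion assumes that ie is read as a specification and that a site may rely on the waiver text over the Table 7 list. It is worth correcting because it concerns a pediatric safety criterion and costs almost nothing to resolve.

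**What to change.** Reconcile Section 7.5.6.4 with Exclusion 6 (Section 3.2 and synopsis) and Table 7:

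- In the waiver, describe the prior results that show a child is not at risk by the markers the protocol already uses to define risk, HBsAg and total anti-HBc.
- In the fallback sentence, make the trigger and the required result refer to those same two markers instead of immune status alone.
- State that the waiver covers only tests with a result on file, so that any Table 7 hepatitis B marker never measured is obtained before enrollment.

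These edits belong in Section 7.5.6.4. The footnotes to Tables 6 and 7 also apply to HIV testing, so hepatitis B wording should not be added there. The change brings in no marker that the exclusion or the panel does not already contain. Beyond the wording, the cost is at most one serology already in the panel, for the few children whose file lacks anti-HBc.

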#### **7.5.6.5. HIV Screening**

Subjects with an active HIV infection are excluded from the study. Prior HIV screening results obtained as standard of care before allo-HSCT confirming the subject is HIV-negative may be used for determining eligibility, and tests do not need to be repeated. Subjects whose HIV status is unknown must have results confirming negative status before enrollment.

#### **7.5.6.6. Adenovirus, EBV, and CMV Assessment**

Assessment of adenovirus, EBV, and CMV viral load (blood DNA PCR) is to be performed at Study Day 1. PCR test results are not required for subject eligibility. Subjects with positive PCR test results will be treated according to the local institutional guidelines.

## 7.6. Efficacy Assessments

### 7.6.1. Acute Graft-Versus-Host Disease Staging and Grading

Acute GVHD grading will be performed by the investigator on a weekly basis for the first 8 weeks after the study start, then every 28 days thereafter. Acute GVHD staging and grading will also occur on Days 100, 180, and 365; at the EOT visit; and during re-treatment (if applicable) and follow-up as indicated in [Table 5](#).

On-treatment aGVHD grading should be performed relative to the Day 1 assessment.

If subjects withdrew due to reasons other than GVHD progression, then GVHD staging and grading will be assessed at the safety follow-up visit and every 28 days thereafter during survival follow-up until progression of GVHD, start of new anti-GVHD therapy, or death.

Data regarding the quantification of aGVHD symptoms (extent of skin rash, total bilirubin level, volume of diarrhea) should be reported using MAGIC guidelines ([Harris et al 2016](#)); response will be assessed as per CIBMTR modifications to the CIBMTR response index as indicated in [Appendix A \(CIBMTR 2009\)](#).

- Skin:
  - Only areas involved with active erythema should be used for determination of BSA staging based on the rule of nines.
  - A portion of a body area segment may be used for the quantification.
  - Desquamation or fluid-filled bullae should be reported if present, as these findings are the hallmark of Stage 4 skin GVHD.
- Liver:
  - Liver GVHD staging is based solely on total (not conjugated/direct) serum bilirubin levels.
  - Liver GVHD manifesting as transaminitis without concomitant elevation in serum bilirubin should be diagnosed when the presence of GVHD is confirmed by liver biopsy (where appropriate) and score it as Stage 0.
  - If bilirubin levels were elevated before the diagnosis of GVHD in another target organ and do not increase further, liver GVHD should not be diagnosed in the absence of biopsy confirmation. However, if hyperbilirubinemia develops at the same time or after the onset of GVHD in another target organ, liver GVHD is presumed to be present in the absence of an identified alternative cause.
- Upper GI:
  - Symptoms of concern for upper GI GVHD include anorexia, nausea, vomiting, and dyspepsia, and assessment depends on close attention to caloric intake and symptom reporting.
  - An upper GI endoscopy should be performed whenever possible to confirm upper GI GVHD; however, the diagnosis may be made without biopsy confirmation.

- GVHD is typically not considered as a possible etiology when nausea lasts fewer than 3 days, or with fewer than 2 vomiting episodes per day for at least 2 days, or anorexia without weight loss.
- Lower GI:
  - Staging of lower GI GVHD relies on accurate measurement of daily stool volumes and documentation of the presence of hematochezia or severe abdominal pain.
  - At the time of GVHD onset, staging should be based on the highest daily volume during the 3 days before diagnosis (excluding volumes attributable to procedures such as bowel preps or endoscopy).
  - After the initiation of treatment, lower GVHD staging should be based on the diarrhea volume using the following measurements (in the order of preference): 1) average of 3 consecutive days, 2) average of 2 consecutive days, or 3) the volume on day of assessment.
  - Severe abdominal pain, ileus, and/or grossly bloody stool should be documented when present, because Stage 4 lower GI GVHD is staged based on the presence of these symptoms and is independent of volume of diarrhea.

